PROTOCOL # GATT CO-161115154122-SACT

PROTOCOL TITLE Human Comedogenicity Test

PROTOCOL IDENTIFICATION : CO-161115154122-SACT

DATE & VERSION : 10 February 2017, Final Version (1.0)

SPONSOR : [REDACTED]
[REDACTED]
[REDACTED]

STUDY SITE : [REDACTED]
[REDACTED]
[REDACTED]
[REDACTED]

PRINCIPAL INVESTIGATOR (PI): [name], FAAD

STUDY MANAGER: [REDACTED]

STUDY DIRECTOR: [REDACTED]

DEPARTMENT HEAD: [REDACTED]

DESIGNATED PHYSICIAN REPRESENTATIVE (DPR): [REDACTED]
[REDACTED]
[REDACTED]
[REDACTED]
[REDACTED]

This study will be performed in compliance with International Conference on Harmonization Guidelines for Good Clinical Practice (E6).

CONFIDENTIAL: The information in this document contains trade secrets and commercial information that are privileged or confidential and may not be disclosed unless such disclosure is required by Federal or State law or regulations. Subject to the foregoing, this information may be disclosed only to those persons involved in the study who have a need to know, but all such persons must be instructed not to further disseminate this information to others. These restrictions on disclosure will apply equally to all future information supplied to you, which is indicated as privileged or confidential.

VERSION TRACKING

VERSION	DATE	STATE	REASON FOR CHANGE	DESCRIPTION OF CHANGE
1.0	10FEB2017	FINAL	New	N/A

SYNOPSIS

PROTOCOL IDENTIFICATION	CO-161115154122-SACT
PROTOCOL TITLE	Human Comedogenicity Test
PRINCIPAL INVESTIGATOR	[name], FAAD
STUDY SITE	████████████████████ ████████████████████ ████████████████████ ████████████████████
OBJECTIVE	To determine the potential of a test material to induce comedones.
STUDY DESIGN	A single center, evaluator blinded, randomized study to test the potential of comedogenicity of test products. The backs of volunteers with a propensity to comedone formation are patched with the test material three times a week for a four-week period. At the last visit, a follicular biopsy is performed on each site of each subject, Microcomedones on the slides are counted and the product categorized as to comedogenic potential.”
STUDY POPULATION	Males and Females aged 18-45 years old who meet the eligibility criteria of the study.
SAMPLE SIZE	Enroll up to 18 volunteers satisfying the inclusion and exclusion criteria. 15 subjects completing the study is sufficient.
INVESTIGATIONAL STUDY MATERIALS	Test Material (TM) information will be provided in protocol addendum for each test panel.
DOSE AND MODE OF APPLICATION	Test materials and Negative Control will be applied with occlusive or semi-occlusive patches. The patch type may be changed if irritation develops. Occlusive patches consist of a non-woven cotton pad (e.g., Webril®) covered by Blenderm tape and held securely to skin on all sides with a porous, hypoallergenic tape (e.g., Micropore®). Semi-occlusive patches consist of a non-woven cotton pad (e.g., Webril®) covered and held securely to skin on all sides with a porous, hypoallergenic tape (e.g., Micropore®). Patches are placed on the back no closer than 2 cm apart. The cotton pads used for the patches

	
are approximately 4 cm² in area, and are dosed with a quantity of test material as follows (unless otherwise instructed by the Sponsor): Liquids and fragrances approximately 100 µl; Creams, lotions, petroleum, etc. approximately 100 µl; Paper or other solid materials will cover the pad area.

STUDY DURATION
	
The study will consist of approximately 13 visits: Visit 1 (Screening/Baseline), Visit 2 through 12: Patching and Grading, Make-up visit, and Visit 13 (Grading and Follicular Biopsy collection visit)

METHODOLOGY
	
Skin sites on the back in the interscapular region will be utilized as application sites. The test material(s) and negative control will be assigned to specific sites for each subject be assigned to specific site for each subject according to a randomization scheme and will be applied repetitively under occlusive/semi-occlusive patches for a period of 28 days.

SAFETY AND ADVERSE EVENTS
	
Any Adverse Event (AE) (including Serious Adverse Events (SAE) related or unrelated to the test material(s) or study participation must be documented as required (occurrence date, site, outcome, and assessment of causality, severity, and relatedness).
 
SAEs must be reported immediately and relevant supportive documentation must be sent to the Study Manager or designee within 24 hours of the site becoming aware of the event.
 
See section 10.3.3. for reporting timelines.

LIST OF ABBREVIATIONS

Abbreviation	Definition
AE	Adverse Event
CRF	Case Report Form
EDC	Electronic Data Capture
ICH GCP	International Conference on Harmonisation Good Clinical Practice
ICD	Informed Consent Document
IEC	Independent Ethics Committee
IP	Investigational Product
IRB	Institutional Review Board
PI	Principal Investigator
PP	Per-Protocol
PQC	Product Quality Complaint
SI	Sub-Investigator

1 BACKGROUND

The human comedogenicity test has been shown to be a predictive method for assessing the comedogenic potential of products intended for use on skin.

2 RATIONALE

This human comedogenicity test panel(s) is being conducted on product(s) making the claim of “non-comedogenic”.

3 OBJECTIVE(S)

The objective of this protocol is to evaluate the comedogenic potential of the test material(s) using the back of human volunteers.

4 OVERALL STUDY DESIGN AND PLAN DESCRIPTION

A single center, evaluator blinded, randomized, four-week clinical test panel(s). This human comedogenicity test panel(s) is being conducted in order to assess the comedogenic potential of the test material(s) and determine if the test material(s) induce microcomedones under repetitive patch test conditions. The target population for each test panel is adult men and women (age 18 through 45 years), who are acne-prone and have large pores on the back and/or a history of acne vulgaris on the face or back. Subjects will be patched on the upper back with test material dosed patches and an undosed occlusive patch (negative control) every Monday, Wednesday, and Friday for 4 consecutive weeks. Each test site will be graded for irritation after each patch removal. After 12 full patching sessions, a follicular biopsy will be collected from the test material and control sites, and graded for microcomedones.

Protocol Activity:	Visit 1 Screening/Baseline	Visit 2- Visit 12 (Conducted Monday Wednesday, and Friday for 4 consecutive weeks) **	Make-up visit* (if needed)	Visit 13
Informed consent with HIPAA disclosure	X			
Collect demographics, general medical history & concomitant medications	X			
Review of potential test sites (upper back) by PI (or designee)	X			
Eligibility review and subject qualification by PI (or medically qualified designee)	X			
Interview for compliance		X	X	X
Remove TM, control, and negative control dosed patches from test sites		X	X	X
Clinical NACDG grading of test sites by PI or designee		X	X	X
Test sites marked (to be remarked as needed)	X	X	X	
Test sites wiped with distilled or deionized water and air dried	X			
Randomization of TM, control, and negative control on test sites	X			
Apply TM, control, and negative control dosed patches on test sites	X	X	X	
Dispense study visit calendar to subject	X			
Review study instructions with subject	X			
Collect follicular biopsy from each test site				X
Collect/record AEs and changes in health/medications	X	X	X	X
Subject disposition				X

* Denoted activity will only occur if subject missed one of the scheduled visits from visits 2 to 12 and requires a make-up visit

** See Study Duration in section 5

5 STUDY DURATION

Each test panel will consist of 13 subject visits: Screening/Baseline (Visit 1) will be completed on either a Monday, Wednesday or Friday, and Visit 2 will be completed 48-72 hours post Visit 1. Visits 3-13 will occur 48-72 hours post each subsequent visit, i.e., Monday, Wednesday, and Friday for four consecutive weeks.

As necessary, a subject may complete a make-up patching visit. Make-up visit will be conducted 48-72 hours post Visit 12. Subject will return to site for Visit 13 for the collection of Follicular Biopsies.

Visit 13 will be conducted 48-72 hours post Visit 12 or post make-up visit if applicable.

Note: 72-hour exposure time is only applicable for visits conducted on Friday and/or to allow for site closed days.

6 SUBJECT SELECTION AND ENROLLMENT

Each study panel can fulfill its objective only if appropriate and required number of subjects is enrolled. The following eligibility criteria are designed to select subjects for whom protocol procedures are considered appropriate. All relevant medical and non-medical conditions should be taken into consideration, in addition to the inclusion/exclusion criteria below, when deciding if a particular individual is suitable for this protocol. The inclusion and exclusion criteria will be reviewed for each subject and confirmed by the Principal Investigator (PI) or a medically qualified individual (MD/DO) at Visit 1 in order to determine subject eligibility for the relevant test panel.

Prior to any review of personal data, Informed Consent documents should be signed.

6.1 INFORMED CONSENT

The Informed Consent Document (ICD), will be read by the subject or explained to the subject by the PI or designee. The PI or designee must ensure that each study subject is fully informed about the nature and objectives of the study and possible risks associated with participation. After understanding and agreeing, the subject will express his/her consent to the subject's participation in the study by signing the ICD.

No subject will be evaluated without a signed ICD, which should be kept by the PI as part of the Site Master File. The ICDs of subjects who are not enrolled in the study will also be part of the Site Master File.

One copy of the signed ICD must be given to the subject; the subject will remain free to withdraw this consent at any moment without any negative consequence to the subject.

The ICD must be approved by the Sponsor and the IRB must be in compliance with ICH GCP, local regulatory requirements, and legal requirements.

In addition to the ICD, an IRB approved Supplemental Consent form may be completed if the subject has indicated that they have previously had eczema and would like to participate in the study. See exclusion criterion VIII.

6.2 STUDY POPULATION

Individuals must meet all of the following eligibility criteria for enrollment into the study.

6.2.1 Inclusion Criteria

Individuals must meet all of the following inclusion criteria for enrollment into the study:

- I. Male or female.
- II. 18 to 45 years old.
- III. Individuals that are willing to provide written informed consent and are able to read, speak, write, and understand English.
- IV. Individuals who are acne-prone with large pores on the back, or individuals who have a history of acne vulgaris on the face or back.
- V. Individuals who have had at least a 2-week rest period since participation in any previous clinical studies involving patch applications on the back.
- VI. Individuals who are willing to avoid direct sun exposure on the back and use of tanning beds for the duration of the study.
- VII. Generally, in good health based on medical history reported by the subject.
- VIII. Have generally healthy skin condition appropriate for study assessments
- IX. Available for the entire study duration.
- X. Individuals who are willing to keep patch sites as dry as possible and refrain from swimming or soaking in a hot tub for the duration of the study (no showering/bathing restrictions).
- XI. Willing to cooperate and follow instructions.
- XII. Female subjects, not of child-bearing potential, must meet at least one of the following criteria:
 - Had a hysterectomy and/or bilateral oophorectomy,
 - Be post-menopausal (amenorrhea for at least 1 year),
 - Had a Tubal Ligation,
 - Surgical sterilization (e.g., tubal occlusion, hysterectomy, bilateral salpingectomy);
- XIII. Female subjects, of child-bearing potential, must agree to practice a medically acceptable form of birth control during the study and 30 days after study completion. Females must have used such birth control for at least 3 months prior to study start;
- XIV. Medically acceptable forms of birth control that may be used by the subject and/or his/her partner include:
 - Established use of hormonal methods of contraception (oral, injected, implanted, patch or vaginal ring).
 - Barrier methods of contraception **with or without** spermicide: condom or occlusive cap (diaphragm or cervical/vault caps),
 - Intrauterine device (IUD) or intrauterine system (IUS),
 - Surgical sterilization (e.g., in a monogamous relationship with male partner with vasectomy that has been confirmed effective by sperm count check, tubal occlusion, hysterectomy, bilateral salpingectomy).
 - Abstinence from heterosexual intercourse: When this is in line with the preferred and usual lifestyle of the subject. Periodic abstinence (e.g., calendar, ovulation, symptothermal, post-ovulation methods) and withdrawal are not acceptable methods of contraception;

6.2.2 Exclusion Criteria

Subjects with any of the hereafter criteria must be excluded from the study:

- I. Individuals with known allergies or sensitivities to common topical skincare products, including adhesives and/or cyanoacrylate (super glue) or ingredients to the test materials for a specific test panel.
- II. Deprived from liberty by a judiciary or administrative decision.
- III. Having undergone organ excision (kidney, lung, spleen, and liver), an organ transplant, or a skull concussion with extended loss of consciousness within the last 5 years or with present symptoms and/or side effects.
- IV. Individuals with self-reported UNCONTROLLED metabolic conditions, such as diabetes, hypertension, hyper/hypothyroidism, hypercholesterolemia, etc.
- V. Individuals with CONTROLLED health conditions may be excluded from the study at the discretion of the PI or designee:
 - Subjects with conditions that do not affect the skin, such as hypertension and hypercholesterolemia, could be enrolled when their health condition is managed through diet, medication, etc.
 - Subjects with conditions, which might affect the skin, such as hyper/hypothyroidism, diabetes must be excluded, regardless whether their health condition is controlled or not.
- VI. Subjects who are taking medication for chronic conditions (e.g., insulin, antihistamines, steroidal and non-steroidal anti-inflammatory drugs, antibiotics, etc...) – exception could be made for hypercholesterolemia as per point IV.
- VII. Individuals with adult asthma and/or epilepsy.
- VIII. Skin diseases on tested sites (e.g., psoriasis, eczema, erythema, edema, scars, wounds, melanomas, etc.), which may influence the outcome of the study;
 - a. Supplemental Consent
During the eligibility screening, individuals who indicate that they have previously had eczema will be advised of the Koebner phenomenon, which refers to the appearance of these conditions either at the patch site or unrelated sites. If the individual chooses to participate in the study, 2 copies of a supplemental consent form will be signed by the subject (1 for the study files and 1 will be given to the subject).
- IX. Subjects who are self-reported to be pregnant, lactating or planning to become pregnant; females of child-bearing potential who are unwilling or unable to use an acceptable method of contraception during the study.
- X. Male subjects who have a pregnant partner.
- XI. Male subjects whose partner is planning to become pregnant during the study period or is unwilling or unable to use an acceptable method of contraception.
- XII. Simultaneous participation in any other type of clinical study.
- XIII. An individual who has any condition which in the PI's judgment makes the candidate an inappropriate subject for study participation.
- XIV. Subjects who are related to those persons involved directly or indirectly with the conduct of this study (i.e., PI, sub-investigators, study coordinators, other site personnel, employees of the Sponsor subsidiaries, contractors of the Sponsor, and the families of each).
- XV. Individuals with a condition or situation which, in the PI's opinion, may put the subject at significant risk, may confound the study results, or may interfere significantly with the subject's participation in the study.
- XVI. Individual viewed by the PI as not being able to complete the study.

XVII. Subjects who are planning to use any new personal care products (e.g. makeup) or are planning to change existing brands during the study

6.3 CONCURRENT PRODUCTS

During the study, subjects will be permitted to follow their normal bathing routine. They will not be permitted to apply any topical product to the patch sites during the span of this study. Subjects should not start using any new personal care products (e.g. makeup, cleanser) or change their currently used brands during the study.

6.4 CONCURRENT MEDICATION

If a subject is taking any medication during the course of the study or within 2 weeks prior to the study, it must be recorded on the Concomitant Medication Form or equivalent. The minimum information required is the name of the medication. If this medication is linked to the treatment of an IP-related AE, dose and duration of the treatment should be specified. Medications excluded are indicated in the Subject Exclusion criteria; the use of any excluded medications during the study will result in discontinuation of the subject.

6.5 SCREENING FAILURE

All individuals who signed ICD and withdraw their participation or fail to meet all of the screening criteria during the initial evaluation will be considered a “screening failure.” These subjects will be replaced (note: screening numbers will not be reused) and their data will not be considered in the final report.

7 SAMPLE SIZE DETERMINATION

A sufficient number of subjects will be screened to enroll as many as 18 qualified subjects to ensure completion of 15 subjects per test panel.

8 INVESTIGATIONAL STUDY MATERIALS

8.1 IDENTITY OF INVESTIGATIONAL STUDY MATERIALS

The test material(s) will be manufactured and packaged by the Sponsor. The ingredient list and Safety Attestation letter for each product will be provided to the PI for review and submission to the IRB. The ingredient list and Safety Attestation letters will be filed in the Site Master File for the test panels.

Formula numbers of the test material(s) will be provided via the protocol addendum form prior to the conduct of each study.

A label will be affixed to each test material. The label may contain (but is not limited to) fields for the following information:

- Reference Number
- Type of test material
- Directions
- Net Contents or Net Weight
- Formula number
- Storage Information
- **“For Investigational Use Only”**

8.2 RANDOMIZATION

Upon qualification and enrollment, each subject will be sequentially issued a subject number starting with "001". Once a subject number has been assigned to a subject, it cannot be reassigned to another subject. The subject numbers will be used to randomly assign the test material(s) and control to the specific test sites for each subject according to a randomization scheme created by the site.

The site will create the randomization scheme for each test panel prior to the initiation of the test panel.

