8.6 APPLICATION OF THE INVESTIGATIONAL PRODUCT

Test materials will be applied using occlusive or semi-occlusive patches. The patch type may be changed during the study if irritation develops. Occlusive patches consist of a non-woven cotton pad (e.g., Webril®) covered by Blenderm tape and held securely to skin on all sides with a porous, hypoallergenic tape (e.g., Micropore®). Semi-occlusive patches consist of a non-woven cotton pad (e.g., Webril®) covered and held securely to skin on all sides with a porous, hypoallergenic tape (e.g., Micropore®). Open patches consist of a non-woven cotton pad (e.g., Webril®) held to the skin on 2 opposing sides by a strip of hypoallergenic tape (e.g., Micropore®). The pad is open on 2 sides like a Band-Aid®.

Patches will be placed on the upper back, to the right and left of the spine. Patches will not be applied closer than 2 centimeters (cm) to each other. The cotton pads used for the patches are approximately 4 cm² in area, and will be dosed with a quantity of test material as follows (unless otherwise instructed by the Sponsor):

- Liquids and fragrances approximately 100 microliters (µL)
- Creams, lotions, petroleum, etc. approximately 100 µL
- Paper, powder or other solid materials a sufficient amount to cover the pad area

Patches will be applied starting at the lower edge of the patch and pressing from below to let air escape. The patch will be secured by gently rubbing the tape (especially the corners) to ensure good adherence.

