9 INVESTIGATIONAL PLAN

9.1 STUDY PROCEDURES AND EVALUATION SCHEDULE

Pre-Study:

Candidate subjects will be recruited using IRB-approved materials. Interested candidates will be scheduled for Visit 1.

Screening/Baseline: Visit 1

Interested candidates will report to the site and take part in the following procedures:

1. Prospective candidates will be sequentially assigned a 2-digit screening number preceded by "S" (e.g. S01).
2. Subjects will be given an IRB-approved ICD and IRB-approved Supplemental Consent form (when applicable) to read and sign. They will have all of their study related questions answered by the Investigator or designated staff, and if they agree, they will sign 2 copies of the ICD and Supplemental Consent form (when applicable). They will retain 1 copy, and 1 will be kept in the study file.
3. Subjects will complete a health and eligibility questionnaire and a medical and medication history questionnaire.
4. Potential test sites (upper back) will be examined by the Investigator or designee for qualification criteria.
5. The screened subjects that meet all eligibility requirements will be enrolled into the study and assigned a subject number as describe in the "Randomization" section.
6. A delegated clinician will delineate up to six test sites on the subject's upper back, to the right and left of the spine, using an indelible marker. Each test site will be a 4 cm² and no closed than 2 cm² from each other. The test sites may be re-delineated at subsequent visits as needed
7. The test sites will be wiped with distilled or deionized water and allowed to air dry prior to patching.
8. The test material dosed patches and an undosed negative control patch will be applied to each subject's upper back according to the predetermined randomization.
9. Subjects will be provided with a calendar of study visits and study instructions. Subjects will be reminded of sun exposure/tanning and swimming/hot tub restrictions. Subjects will also be instructed to reinforce the edges of the patch with a bandage tape in the event that the tape applied in the clinic does not adhere.

Interim Visits: Visit 2 – Visit 12

Visit 2 will be completed 48-72 hours post Visit 1. Visits 3-12 will occur 48-72 hours post each subsequent visit, i.e., Monday, Wednesday, and Friday for four consecutive weeks. Subjects will report to the site at their scheduled visit time and will participate in the following procedures at each interim visit:

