Demographic data and baseline characteristics will be summarized for all subjects who are enrolled in the study. For continuous variables, descriptive statistics including number of subjects (N), mean, median, standard deviation (SD), minimum (MIN) and maximum (MAX) values will be presented. For categorical variables, the frequency and percentage of each category will be provided.

A descriptive statistical summary will be provided for the global assessments of microcomedone data from biopsies for the test material and control sites. The descriptive statistical summary includes the number of observations (N), mean, median, standard deviation (SD), minimum (MIN), and maximum

(MAX).

In addition, microcomedone scores will be analyzed using a mixed-effects model, where the test Material/negative control is a fixed effect and the subject is a random effect. Each test product will be compared to the negative control within the model frame. A test material will be considered positive for comedogenicity if it has a mean microcomedone value of 1.0 or greater, and is statistically greater than the mean microcomedone value for the negative control site.

All statistical tests will be 2-sided at significance level $\alpha=0.05$. P-values will be reported to 3 decimal places (0.000). No multiple testing corrections will be considered in the study. Statistical analyses are performed using SAS software version 9.30 or later series (SAS Statistical Institute). The results will be sent to the Sponsor along the raw data in a Microsoft Excel document at the completion of the study.

A test material is considered negative for comedogenicity as long as it satisfies 1 of the following 2 conditions: the microcomedone mean score is less than 1.0 and/or the mean score is not greater than the control with p-value < 0.05 .

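### Balance over back positions is not specified and position is not in the model; specifying both together is a cheap, optional gain in precision

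*Combined protocol and SAP*

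**What the plan says.** Section 8.2 uses the subject number to allocate materials and control to back positions at random, "according to a randomization scheme created by the site". On timing it adds: "The site will create the randomization scheme for each test panel prior to the initiation of the test panel". It neither requires nor rules out balance over positions.

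On layout, section 9.1 says "A delegated clinician will delineate up to six test sites on the subject's upper back", and section 8.6 says "Patches will be placed on the upper back, to the right and left of the spine". The number of materials in a panel is left to an addendum, so six sites is a maximum. No arrangement in rows is described.

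Section 10 specifies a mixed-effects model "where the test Material/negative control is a fixed effect and the subject is a random effect", and "Each test product will be compared to the negative control within the model frame". There is no position term. Tests are two-sided at 0.05. A material is positive only if its mean score is at least 1.0 and it is significantly above the negative control. Failing either condition makes it negative.

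Section 7 plans up to 18 enrolled to obtain 15 completers per panel and gives no SD, effect size or power. Section 10 analyses completers only.

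**The concern.** Position on the back is a design factor that the randomization list fixes and records for every slide. The subject effect removes differences between people, but not differences between positions within a person. If some positions yield more microcomedones than others, that difference is left in the residual of a small test.

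The direction of the loss matters here. Section 2 says the panels are run on products making a non-comedogenic claim, and a non-significant difference from control is sufficient for a negative result. A wider standard error therefore makes the favourable conclusion easier to reach. All materials in a panel are compared with the same control site, so the control's placement enters every comparison.

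**Working it through.** **Plan's own figure.** The plan gives no power to reproduce. Going from 18 enrolled to 15 completers allows for a loss of 3/18 = 16.7%.

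**Inputs from the documents.** n = 15 completers (section 7); up to k = 6 sites (section 9.1); two-sided alpha 0.05 and a material-plus-subject model (section 10).

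**Assumptions, not in the documents.** Residual SD 0.5; true product-control difference 0.5; scores treated as normal; unrestricted within-subject randomization; six sites in three rows of two, with row effects -g, 0 and +g.

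**Standard error without a position term.** Under unrestricted randomization the position variance adds to the residual:

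SE = sqrt(2 x (0.5^2 + S^2)/15), where S^2 = 4g^2/5 is the variance of the six position effects (divisor k-1).

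- g = 0: S^2 = 0; SE = sqrt(2 x 0.250/15) = 0.183
- g = 0.2: S^2 = 0.032; SE = sqrt(2 x 0.282/15) = 0.194
- g = 0.4: S^2 = 0.128; SE = sqrt(2 x 0.378/15) = 0.224

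**Degrees of freedom.** The residual has 90 - 1 - 14 - 5 = 70, or 65 with position added. The t critical value goes from 1.994 to 1.997 (+0.14%). With two sites it is 14 to 13, and 2.145 to 2.160 (+0.7%).

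**Power**, approximately Phi(0.5/SE - t critical):

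| Gradient | Plan's model, unrestricted list | Balanced list plus position term |
|---|---|---|
| none | Phi(2.74 - 1.99) = 77% | Phi(2.74 - 2.00) = 77% |
| +/-0.2 | Phi(2.58 - 1.99) = 72% | 77% |
| +/-0.4 | Phi(2.23 - 1.99) = 59% | 77% |

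Simulation of whole panels agrees: SE 0.181, 0.192 and 0.224 for the plan against 0.182 after the fix, with power about 60% against 77% at +/-0.4.

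**The same result in terms of position SD.** The SE is multiplied by sqrt(1 + position variance/residual variance). This gives +2% at position SD 0.1, +12% at 0.25 and +41% at 0.5. Normal-approximation power is 78% with no effect, then 77%, 69% and 49%.

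**Validity.** With unrestricted allocation and no true difference, the simulated upper-tail error stayed between 1.5% and 3.5%, around the nominal 2.5%. The reported SE tracked the true one.

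**Either change alone** (six sites, simulated, 1,500 runs per setting):

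- Balanced list without the term, position SD 0.5: the true SE falls to 0.19, but the model still reports 0.26. Upper-tail error drops to 0.4% and power is 44%, so the test gains nothing.
- Term added to an unrestricted list: power rises from 48% to 75% at position SD 0.5, but falls from 76% to 73% if position has no effect. With two sites and no effect it falls from 74% to 70%.

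**The case against.** Four points on the other side are fair.

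First, a reader might infer that the allocation is unbalanced. The documents do not show that. The site writes the list in advance, and a Latin square would comply with section 8.2. What is missing is a requirement. Even if the site balances, the model omission in section 10 remains, and balance without the term does not help the test.

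Second, no position effect is documented. All sites lie in one region, which the synopsis calls interscapular. The 60% power figure needs a spread of 0.8 grade between the extreme rows, which is larger than the assumed product effect of 0.5. At position SD 0.1 the loss is about 2% in SE.

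Third, a reader might infer that chance imbalance makes the comparisons biased or the 1.0 cut-off unreliable. Randomization keeps the comparisons unbiased. The chance shift in one product's mean has SD sqrt((4g^2/6)/15), which is 0.04 at g = 0.2 and 0.08 at g = 0.4. Ordinary sampling error is 0.5/sqrt(15) = 0.13. The shift can go either way and is the smaller source of error near the cut-off.

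Fourth, the change is not entirely free. Only completers are analysed, and section 9.2 allows a biopsy to be omitted at a site with an irritation grade of 2 or more. Fifteen is not a multiple of 2, 4 or 6. Balance among the analysed slides may therefore be only approximate.

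All four stand. They limit the point to precision, of unknown size, and leave the recommendation intact.

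**Conclusion.** The point holds as a conditional loss of precision. The plan does not specify balance over positions and leaves position out of the model, so any position variance widens every product-control comparison. Under the stated assumptions, the SE is 6% larger at +/-0.2 (0.194/0.183) and 23% larger at +/-0.4 (0.224/0.183), and unchanged if positions do not differ. Power is about 72%, 60% and 77% respectively, against about 77% throughout with the fix.

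The residual SD, the difference, the six-site row layout, the gradient and the unrestricted list are all assumptions. The documents support no claim that positions do differ, that the site's list is unbalanced, or that the test is invalid. The reason to act is that the remedy is cheap and that imprecision favours a negative call. Severity: optional.

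**What to change.** Make both changes together.

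- **Section 8.2:** require the list for each panel to be built from Latin-square blocks, so that each material and the control appear at each position as equally often as the number of sites and completers allows.
- **Section 10:** add site position as a fixed effect beside material, with subject random.

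**Cost.** A different list, which the site already prepares before each panel, and one model term using k-1 degrees of freedom (70 to 65 with six sites). With a near-balanced list this is about one power point or less. If balance is lost and position has no effect, it is about 3 to 5 points. Balance can only be approximate for 2, 4 or 6 sites with 15 completers, and for 4 sites even with all 18 enrolled.
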